3.10.2 Laboratory Evaluations

Hematology and serum chemistries will be summarized using summary statistics for the following values by cohort and overall: baseline value, minimum and maximum post-baseline values, average post-baseline value, and last post-baseline value. Change from baseline for each of these post-baseline values will also be summarized.

Whenever available, laboratory values will be assigned toxicity grades using the NCI-CTCAE, version 4.03. Shifts in laboratory values to outside the local laboratory normal range will be evaluated for selected laboratory tests by assessing, relative to the baseline value, the maximum increase and/or decrease observed throughout the course of study treatment, and the last reported value. The number and proportion of patients with directional shifts above or below the normal range will be summarized for selected laboratory tests. Similar analyses will be performed for shifts in NCI CTCAE toxicity grades relative to the baseline toxicity grade.

Percentages will be based on the total number of patients with a baseline assessment and at least one post-baseline assessment for the given laboratory parameter. Laboratory test groupings and standard normal ranges are described in [Appendix 5.1](#), and CTCAE toxicity grades for hematology and chemistry parameters are described in [Appendix 5.2](#) and [Appendix 5.3](#), respectively.

Listings of all clinical laboratory data for each patient will be provided. A separate listing of all out of normal range as well as all toxicity grade values will also be provided.

3.10.3 Vital Signs

Change from baseline for vital signs (temperature, pulse, systolic/diastolic blood pressure, respiration rate, and weight) will be summarized over time by treatment group and overall.

A patient listing of all vital sign assessments will be provided.

3.10.4 ECG

Electrocardiogram results will be listed and summarized in terms of the number and percentage of patients with abnormal and normal findings, as reported by the Investigator, at the time points where ECGs were assessed.

3.11 Pharmacokinetic Analysis

A population PK analysis will be used to describe the PK of entinostat. The effects of patient factors (e.g., demographics, clinical chemistries, and disease) on entinostat PK will be evaluated. In addition, the relationship between entinostat exposure parameters and indicators of safety will be assessed. Descriptive statistics will be used to summarize the PK of avelumab and anti-avelumab antibodies at each cycle and time point.

Specific details for these analyses as well as analyses of trough avelumab levels and anti-avelumab antibodies will be provided in a separate analysis plan.

3.12 Correlative Analysis

Immune correlate values will be summarized in a descriptive manner. For immune correlates measured on a continuous scale, the number of patients with non-missing data, mean, standard error or standard deviation, median, 25th percentile (first quartile), 75th percentile (third quartile), minimum, and maximum values will be presented. For discrete data, the frequency and percent distribution will be presented. [REDACTED]

[REDACTED]

[REDACTED]

[REDACTED] Additionally, the correlation among the various initial immune correlate values may be assessed by calculating Spearman's correlation coefficient. Analysis of covariance models may be used to explore the relationship between changes in immune correlates and selected measures of antineoplastic activity (e.g., maximum change from baseline in the sum of product diameters in measurable lesions).

5 APPENDIX

5.1 Laboratory Test Groupings and Standard Normal Range

Analyte	Standard Unit	Significant Digits	Directional Change of Interest	Standard Normal Range [†]
Lab group = Hematology, WBC with Differential				
WBC count [‡]	10 ⁹ cells/L	XX.X	Decrease	3.2 – 9.8
Basophil count	10 ⁶ cells/L	XX	Decrease	15 – 50
Eosinophil count	10 ⁶ cells/L	XXX	Decrease	50 – 250
Lymphocyte count [‡]	10 ⁶ cells/L	XXXX	Decrease	1500 – 3000
Monocyte count	10 ⁶ cells/L	XXX	Decrease	285 – 500
Neutrophil count [‡]	10 ⁶ cells/L	XXXX	Decrease	3000 – 5800
Lab group = Hematology, Erythrocytes and Platelets				
Hematocrit	Fraction of 1.00	0.XX	Decrease	0.33 – 0.43 (female)
				0.39 – 0.49 (male)
Hemoglobin [‡]	g/L	XXX	Decrease	115 – 155 (female)
				140 – 180 (male)
RBC count	10 ¹² /L	X.X	Decrease	3.5 – 5.0
Platelet count [‡]	10 ⁹ /L	XXX	Decrease	130 – 400
Lab group = Hematology, Coagulation				
PT	seconds	XX	Increase	9 – 12
PTT [‡]	seconds	XX	Increase	22 – 37

[†] Standard normal ranges are provided for reference and not will be used in analysis unless laboratory normal ranges are missing. Source: Laposta, M: *SI Unit Conversion Guide*, The New England Journal of Medicine Books, Boston, 1992.

[‡] If present, indicates CTCAE toxicity grade is defined for the analyte.

Laboratory Test Groupings and Standard Normal Range (continued)

Analyte	Standard Unit	Significant Digits	Directional Change of Interest	Standard Normal Range [†]
Lab group = Chemistry, Hepatic				
Albumin [‡]	g/L	XX	Decrease	40 – 60
Alk Phos [‡]	U/L	XXX	Increase	30 – 120
ALT [‡]	U/L	XXX	Increase	0 – 35
AST [‡]	U/L	XXX	Increase	0 – 35
Lactic dehydrogenase	U/L	XXX	Increase	50 – 150
Total Bilirubin [‡]	micromol/L	XX	Increase	2 – 18
Total Protein	g/L	X.XX	Decrease	60 – 80
Lab group = Chemistry, Renal				
BUN	mmol/L of urea	X.X	Increase	3.0 – 6.5
Creatinine [‡]	micromol/L	XXX	Increase	50 – 110
Creatinine clearance	mL/min	XXX	Decrease	75 – 125

[†] Standard normal ranges are provided for reference and not will be used in analysis unless laboratory normal ranges are missing.

Source: Laposta, M: *SI Unit Conversion Guide*, The New England Journal of Medicine Books, Boston, 1992.

[‡] If present, indicates CTCAE toxicity grade is defined for the analyte.

Laboratory Test Groupings and Standard Normal Range (continued)

Analyte	Standard Unit	Significant Digits	Directional Change of Interest	Standard Normal Range [†]
Lab group = Chemistry, Electrolytes				
Bicarbonate [‡]	mmol/L	XX	Both	22 – 28
Calcium [‡]	mmol/L	X.XX	Both	2.20 – 2.56
Chloride	mmol/L	XXX	Both	95 – 105
Magnesium [‡]	mmol/L	X.XX	Both	0.80 – 1.20
Phosphorus	mmol/L	X.XX	Both	0.80 – 1.60
Potassium [‡]	mmol/L	X.X	Both	3.5 – 5.0
Sodium [‡]	mmol/L	XXX	Both	135 – 147
Lab group = Chemistry, Metabolic				
Glucose [‡]	mmol/L	XX.X	Both	3.9 – 6.1
Uric Acid	micromol/L	XXX	Increase	120 – 420

[†] Standard normal ranges are provided for reference and not will be used in analysis unless laboratory normal ranges are missing.

Source: Laposta, M: *SI Unit Conversion Guide*, The New England Journal of Medicine Books, Boston, 1992.

[‡] If present, indicates CTCAE toxicity grade is defined for the analyte.

5.2 CTCAE Toxicity Grades: Hematology

Analyte	Standard Unit	Directional Change of Interest	Toxicity Grades (CTCAE v4.03)
WBC with Differential			
WBC count	$10^9/\text{L}$	Decrease	Grade 0: $\geq \text{LLN}$ Grade 1: $< \text{LLN} - 3.0 \times 10^9/\text{L}$ Grade 2: $< 3.0 - 2.0 \times 10^9/\text{L}$ Grade 3: $< 2.0 - 1.0 \times 10^9/\text{L}$ Grade 4: $< 1.0 \times 10^9/\text{L}$
Lymphocyte count	10^6 cells/L	Decrease	Grade 0: $\geq \text{LLN}$ Grade 1: $< \text{LLN} - 0.8 \times 10^6/\text{L}$ Grade 2: $< 0.8 - 0.5 \times 10^6/\text{L}$ Grade 3: $< 0.5 - 0.2 \times 10^6/\text{L}$ Grade 4: $< 0.2 \times 10^6/\text{L}$
Neutrophil count	10^6 cells/L	Decrease	Grade 0: $\geq \text{LLN}$ Grade 1: $< \text{LLN} - 1.5 \times 10^6/\text{L}$ Grade 2: $< 1.5 - 1.0 \times 10^6/\text{L}$ Grade 3: $< 1.0 - 0.5 \times 10^6/\text{L}$ Grade 4: $< 0.5 \times 10^6/\text{L}$

LLN=lower limit of normal. ULN=upper limit of normal. The LLN and ULN for each analyte will be determined from the normal range of each local laboratory.

CTCAE Toxicity Grades: Hematology (continued)

Analyte	Standard Unit	Directional Change of Interest	Toxicity Grades (CTCAE v4.03)
Erythrocytes and Platelets			
Hemoglobin	g/L	Decrease	Grade 0: \geq LLN Grade 1: $<$ LLN – 100 g/L Grade 2: $<$ 100 – 80 g/L Grade 3: $<$ 80 g/L Grade 4: Not defined
Platelet count	10^9 /L	Decrease	Grade 0: \geq LLN Grade 1: $<$ LLN – 75×10^9 /L Grade 2: $<$ 75 – 50×10^9 /L Grade 3: $<$ 50 – 25×10^9 /L Grade 4: $<$ 25×10^9 /L
Coagulation			
PTT	seconds	Increase	Grade 0: \leq ULN Grade 1: $>$ ULN – $1.5 \times$ ULN Grade 2: $>$ $1.5 - 2.5 \times$ ULN Grade 3: $>$ $2.5 \times$ ULN Grade 4: Not defined

LLN=lower limit of normal. ULN=upper limit of normal. The LLN and ULN for each analyte will be determined from the normal range of each local laboratory.

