3.3.3 Safety Variables

Safety variables include:

- Determination of DLT, MTD and RP2D
- Incidence of TEAEs:

TEAEs are defined as any AE occurring or worsening in severity after the administration of study drug. TEAEs will be categorized as:

- Relationship to entinostat
- Relationship to avelumab
- Severity/Grade according to National Cancer Institute Terminology Criteria for Adverse Events (NCI CTCAE) Version 4.03
- Action with respect to entinostat
- Action with respect to avelumab
- Seriousness and outcome

- Change in chemistry and hematology parameters from baseline to minimum and maximum post-baseline values, average post-baseline value, and last post-baseline value
- Shifts in chemistry and hematology parameters from baseline to worst post-baseline in CTCAE toxicity grade
- Shifts in chemistry and hematology parameters outside the laboratory normal range from baseline to maximum increase and/or decrease, and last post-baseline value
- Change from baseline in vital signs and weight at each post-baseline time point
- Change from baseline in 12-lead ECG parameters at each post-baseline time point
- Change from baseline in ECOG at each post-baseline time point

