Table 14.4.5.3	Treatment-Emergent Adverse Events with Severity of Grade 3 or Greater and Judged Related to Entinostat – Phase 2 (Safety)
Table 14.4.5.4	Treatment-Emergent Adverse Events with Severity of Grade 3 or Greater and Judged Related to Avelumab – Phase 2 (Safety)
Table 14.4.6.1	Treatment-Emergent Adverse Events Occasioning Treatment Modification of Any Study Drug – Phase 2 (Safety)
Table 14.4.6.1.1	Treatment-Emergent Adverse Events Occasioning Treatment Modification of Any Study Drug – Phase 1b (Safety)

Table 14.4.6.2	Treatment-Emergent Adverse Events Occasioning Treatment Modification of Entinostat Alone – Phase 2 (Safety)
Table 14.4.6.3	Treatment-Emergent Adverse Events Occasioning Treatment Modification of Avelumab Alone – Phase 2 (Safety)
Table 14.4.7.1	Serious Treatment-Emergent Adverse Events by Preferred Term – Phase 2 (Safety)
Table 14.4.7.2	Serious Treatment-Emergent Adverse Events by Preferred Term and Judged Related to Any Study Drug – Phase 2 (Safety)
Table 14.4.7.3	Serious Treatment-Emergent Adverse Events by Preferred Term and Judged Related to Entinostat – Phase 2 (Safety)
Table 14.4.7.4	Serious Treatment-Emergent Adverse Events by Preferred Term and Judged Related to Avelumab – Phase 2 (Safety)
Table 14.4.8.1	Hematology Laboratory Values – Phase 2 (Safety)
Table 14.4.8.2	Chemistry Laboratory Values – Phase 2 (Safety)
Table 14.4.9.1	Abnormal Hematology Laboratory Values According to the Local Laboratory Normal Range – Phase 2 (Safety)
Table 14.4.9.2	Abnormal Chemistry Laboratory Values According to the Local Laboratory Normal Range – Phase 2 (Safety)
Table 14.4.10.1	Abnormal Hematology Laboratory Values by Cycle According to the CTCAE Toxicity Grade – Phase 2 (Safety)

Table 14.4.10.2	Abnormal Chemistry Laboratory Values by Cycle According to the CTCAE Toxicity Grade – Phase 2 (Safety)
Table 14.4.11.1	Hematology Laboratory Value Shifts from Baseline According to the Local Laboratory Normal Range – Phase 2 (Safety)
Table 14.4.11.2	Chemistry Laboratory Value Shifts from Baseline According to the Local Laboratory Normal Range – Phase 2 (Safety)
Table 14.4.12.1	Hematology Laboratory Value Shifts from Baseline According to the CTCAE Toxicity Grade – Phase 2 (Safety)
Table 14.4.12.2	Chemistry Laboratory Value Shifts from Baseline According to the CTCAE Toxicity Grade – Phase 2 (Safety)
Table 14.3.15	Vital Signs – Phase 2 (Safety)
Table 14.3.16	12-Lead Electrocardiogram Normality by Assessment –

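### Appendix 5.2 gives the neutrophil and lymphocyte grade limits 1000-fold too low, so almost every Grade 2–4 value would be programmed as Grade 1

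*SAP*

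**What the plan says.** Section 3.10.2 sets the grading rule: "Whenever available, laboratory values will be assigned toxicity grades using the NCI-CTCAE, version 4.03". It then sends the reader to the appendices for the limits: "CTCAE toxicity grades for hematology and chemistry parameters are described in" Appendix 5.2 (hematology) and Appendix 5.3 (chemistry).

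Appendix 5.2 lists neutrophils and lymphocytes with the unit 10^6 cells/L. Its Grade 2 lines are:

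- neutrophils: "Grade 2: $< 1.5 - 1.0 \times 10^6/\text{L"
- lymphocytes: "Grade 2: $< 0.8 - 0.5 \times 10^6/\text{L"

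The neutrophil Grade 4 line is "Grade 4: $< 0.5 \times 10^6/\text{L". The WBC row of the same table is on the 10^9/L scale; its Grade 4 line is "Grade 4: $< 1.0 \times 10^9/\text{L".

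Appendix 5.1 also gives both analytes in 10^6 cells/L, in a four-digit whole-number format, with standard normal ranges of 3000–5800 (neutrophils) and 1500–3000 (lymphocytes).

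Section 3.3.3 lists as a safety variable: "Shifts in chemistry and hematology parameters from baseline to worst post-baseline in CTCAE toxicity grade". The matching output in Section 6.1 is Table 14.4.12.1, "Hematology Laboratory Value Shifts from Baseline According to the CTCAE Toxicity Grade". Table 14.4.10.1 (grades by cycle) and Listing 16.2.3.11 also use the grades.

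**The concern.** The normal ranges and the grade limits carry the same unit but differ by three orders of magnitude. With a lower limit of normal of 3000 and a Grade 2 limit of 1.5, Grade 1 for neutrophils would run from just under 3000 down to 1.5 ×10^6/L, which takes in nearly every abnormally low count a laboratory could report.

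The error would pass silently. Unit column and limits agree in unit, the code would run, and the output would look like a benign profile. The neutrophil and lymphocyte rows would show almost no Grade 2–4 results in either arm and so could not show a difference between arms in graded neutropenia or lymphopenia. Clinical laboratory parameters are one of the two measures named in the safety objective (Section 2.1.2), and the error runs towards understating toxicity.

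**Working it through.** **Inputs.**

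| Item | Neutrophils | Lymphocytes | Source |
|---|---|---|---|
| Unit | 10^6 cells/L | 10^6 cells/L | App. 5.1, 5.2 |
| Standard lower limit of normal (LLN) | 3000 | 1500 | App. 5.1 |
| Grade 2 / 3 / 4 upper limits as printed (×10^6/L) | 1.5 / 1.0 / 0.5 | 0.8 / 0.5 / 0.2 | App. 5.2 |
| Same numerals read as ×10^9/L, in ×10^6/L | 1500 / 1000 / 500 | 800 / 500 / 200 | printed × 1000 |

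**Step 1: is the unit wrong, or the limits?** Add the five differential ranges in Appendix 5.1 (basophils, eosinophils, lymphocytes, monocytes, neutrophils), all in 10^6/L:

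- lower: 15 + 50 + 1500 + 285 + 3000 = 4850, i.e. 4.85 ×10^9/L
- upper: 50 + 250 + 3000 + 500 + 5800 = 9600, i.e. 9.60 ×10^9/L

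This lies inside the printed WBC range of 3.2–9.8 ×10^9/L. The 10^6 unit is therefore right for the counts, and the grade limits are what is off.

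**Step 2: LLN against the Grade 2 limit.**

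- Neutrophils: 3000 / 1.5 = 2000 as printed; 3000 / 1500 = 2.0 rescaled.
- Lymphocytes: 1500 / 0.8 = 1875 as printed; 1500 / 800 = 1.875 rescaled.

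**Step 3: WBC cross-check, using no LLN.** WBC Grade 4 is below 1.0 ×10^9/L = 1000 ×10^6/L. Neutrophils are part of WBC, so a patient at WBC Grade 4 has a neutrophil count of at most 999 ×10^6/L in whole numbers. On the rescaled limits all 1000 values from 0 to 999 are neutrophil Grade 3 or 4. As printed, 998 of the 1000 are Grade 1, the value 1 is Grade 2, and only the value 0 is Grade 4. The WBC Grade 4 limit divided by the neutrophil Grade 4 limit is 1000 / 0.5 = 2000 as printed and 1000 / 500 = 2 rescaled.

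**Step 4: grade every whole-number count both ways.**

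- Neutrophils 0–1499 (Grade 2–4 rescaled): 1498 of 1500 = 99.9% are Grade 1 as printed. The exceptions are 0 (Grade 4) and 1 (Grade 2).
- Lymphocytes 0–799 (Grade 2–4 rescaled): 799 of 800 = 99.9% are Grade 1 as printed. The exception is 0 (Grade 4).

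| Count (×10^6/L) | Grade as printed | Grade rescaled |
|---|---|---|
| Neutrophils 1200 | 1 | 2 |
| Neutrophils 900 | 1 | 3 |
| Neutrophils 400 | 1 | 4 |
| Lymphocytes 700 | 1 | 2 |
| Lymphocytes 400 | 1 | 3 |
| Lymphocytes 100 | 1 | 4 |

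**Step 5: could this be a reading fault in the PDF text?** Unlikely. The exponent 6 stands in both unit cells and in all four of the Grade 1–4 lines of each analyte, while the WBC and platelet rows of the same table show 10^9.

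**The case against.** The strongest reply is that the governing rule is right. Section 3.10.2 and the column header of Appendix 5.2 both name CTCAE v4.03, so the appendix only transcribes an outside standard. A careful programmer would go to that standard, and separate programming specifications (Section 3.1.1) may already hold the right limits. The slip is also conspicuous: four-digit counts would be graded against 1.5 or 0.8, beside WBC grades that behave normally.

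The reach is limited too. The primary endpoint is PFS. The DSMB safety reviews in Section 2.3.1 focus on deaths, treatment modifications and discontinuations, and SAEs. Minimum and last values, changes from baseline, normal-range shifts, listings and Grade 3 or greater adverse events would still show a signal, and regrading needs only a program correction. Section 3.10.2 restricts the normal-range shift summaries to selected tests that it does not name, with similar analyses for grade shifts, so neutrophil and lymphocyte rows in Table 14.4.12.1 are likely rather than stated.

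The limits on reach stand, and the consequence is conditional on the appendix being followed. Naming v4.03 does not settle the matter, though. Section 3.10.2 points to the appendices for the grades, and Appendix 5.2 carries no caveat of the kind attached to the normal ranges in Appendix 5.1, which are given for reference and used only when local ranges are missing. Appendix 5.3 openly takes its bicarbonate grades from CTCAE v3.0, so a programmer cannot treat every departure from v4.03 as a mistake to override.

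**Conclusion.** The appendix is wrong as written: both rows are 1000-fold too low, and this can be shown from the SAP alone. If followed, almost every neutrophil or lymphocyte value that should be Grade 2–4 is reported as Grade 1.

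The 99.9% figures assume that the local LLN is above 1500 (neutrophils) and 800 (lymphocytes) ×10^6/L; the printed standard lower limits are 3000 and 1500. They weight every possible whole number equally, and the SAP gives no basis for an expected number of misgraded patients.

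The damage is confined to laboratory-derived grades for these two analytes. The WBC, hemoglobin and platelet grades are on a consistent scale. The error should be corrected before programming, because it sits in the specification for a listed safety variable.

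**What to change.** In Appendix 5.2, restate the Grade 2/3/4 limits in the unit of the analysis variable, with the lower bound of Grade 1 to match:

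- neutrophils: 1500 / 1000 / 500 ×10^6/L
- lymphocytes: 800 / 500 / 200 ×10^6/L

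Alternatively, keep the printed numerals, label them ×10^9/L, and state the conversion from 10^6/L. In either case, convert each local LLN to the same unit before grading, and check both rows against the cited CTCAE v4.03. If programming specifications already exist, check the same two analytes there.

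The cost is two appendix rows. No new data are needed, and the design and the efficacy analyses do not change.

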5.3 CTCAE Toxicity Grades: Chemistry

Analyte	Standard Unit	Directional Change of Interest	Toxicity Grades (CTCAE v4.03)
Hepatic			
Albumin	g/L	Decrease	Grade 0: \geq LLN Grade 1: $<$ LLN – 30 g/L Grade 2: $<$ 30 – 20 g/L Grade 3: $<$ 20 g/L Grade 4: Not defined
Alk Phos	U/L	Increase	Grade 0: \leq ULN Grade 1: $>$ ULN – 2.5 \times ULN Grade 2: $>$ 2.5 – 5.0 \times ULN Grade 3: $>$ 5.0 – 20.0 \times ULN Grade 4: $>$ 20.0 \times ULN
ALT	U/L	Increase	Grade 0: \leq ULN Grade 1: $>$ ULN – 3.0 \times ULN Grade 2: $>$ 3.0 – 5.0 \times ULN Grade 3: $>$ 5.0 – 20.0 \times ULN Grade 4: $>$ 20.0 \times ULN

LLN=lower limit of normal. ULN=upper limit of normal. The LLN and ULN for each analyte will be determined from the normal range of each local laboratory.

CTCAE Toxicity Grades: Chemistry (continued)

Analyte	Standard Unit	Directional Change of Interest	Toxicity Grades (CTCAE v4.03)
Hepatic (continued)			
AST	U/L	Increase	Grade 0: \leq ULN Grade 1: $>$ ULN – $3.0 \times$ ULN Grade 2: $> 3.0 - 5.0 \times$ ULN Grade 3: $> 5.0 - 20.0 \times$ ULN Grade 4: $> 20.0 \times$ ULN
Total Bilirubin	micromol/L	Increase	Grade 0: \leq ULN Grade 1: $>$ ULN – $1.5 \times$ ULN Grade 2: $> 1.5 - 3.0 \times$ ULN Grade 3: $> 3.0 - 10.0 \times$ ULN Grade 4: $> 10.0 \times$ ULN
Renal			
Creatinine	micromol/L	Increase	Grade 0: \leq ULN Grade 1: $>$ ULN – $1.5 \times$ ULN Grade 2: $> 1.5 - 3.0 \times$ ULN Grade 3: $> 3.0 - 6.0 \times$ ULN Grade 4: $> 6.0 \times$ ULN

LLN=lower limit of normal. ULN=upper limit of normal. The LLN and ULN for each analyte will be determined from the normal range of each local laboratory.

CTCAE Toxicity Grades: Chemistry (continued)

Analyte	Standard Unit	Directional Change of Interest	Toxicity Grades (CTCAE v4.03)
Electrolytes			
Sodium	mmol/L	Increase	Grade 0: \leq ULN Grade 1: $>$ ULN – 150 mmol/L Grade 2: $>$ 150 – 155 mmol/L Grade 3: $>$ 155 – 160 mmol/L Grade 4: $>$ 160 mmol/L
		Decrease	Grade 0: \geq LLN Grade 1: $<$ LLN – 130 mmol/L Grade 2: Not defined Grade 3: $<$ 130 – 120 mmol/L Grade 4: $<$ 120 mmol/L
Potassium	mmol/L	Increase	Grade 0: \leq ULN Grade 1: $>$ ULN – 5.5 mmol/L Grade 2: $>$ 5.5 – 6.0 mmol/L Grade 3: $>$ 6.0 – 7.0 mmol/L Grade 4: $>$ 7.0 mmol/L
		Decrease	Grade 0: \geq LLN Grade 1: $<$ LLN – 3.0 mmol/L Grade 2: Not defined Grade 3: $<$ 3.0 – 2.5 mmol/L Grade 4: $<$ 2.5 mmol/L

LLN=lower limit of normal. ULN=upper limit of normal. The LLN and ULN for each analyte will be determined from the normal range of each local laboratory.

CTCAE Toxicity Grades: Chemistry (continued)

Analyte	Standard Unit	Directional Change of Interest	Toxicity Grades (CTCAE v4.03)
Electrolytes (continued)			
Magnesium	mmol/L	Increase	Grade 0: \leq ULN Grade 1: $>$ ULN – 1.23 mmol/L Grade 2: Not defined Grade 3: $>$ 1.23 – 3.30 mmol/L Grade 4: $>$ 3.30 mmol/L
		Decrease	Grade 0: \geq LLN Grade 1: $<$ LLN – 0.5 mmol/L Grade 2: $<$ 0.5 – 0.4 mmol/L Grade 3: $<$ 0.4 – 0.3 mmol/L Grade 4: $<$ 0.3 mmol/L
Calcium	mmol/L	Increase	Grade 0: \leq ULN Grade 1: $>$ ULN – 2.9 mmol/L Grade 2: $>$ 2.9 – 3.1 mmol/L Grade 3: $>$ 3.1 – 3.4 mmol/L Grade 4: $>$ 3.4 mmol/L
		Decrease	Grade 0: \geq LLN Grade 1: $<$ LLN – 2.0 mmol/L Grade 2: $<$ 2.0 – 1.75 mmol/L Grade 3: $<$ 1.75 – 1.5 mmol/L Grade 4: $<$ 1.5 mmol/L

LLN=lower limit of normal. ULN=upper limit of normal. The LLN and ULN for each analyte will be determined from the normal range of each local laboratory.

CTCAE Toxicity Grades: Chemistry (continued)

Analyte	Standard Unit	Directional Change of Interest	Toxicity Grades (CTCAE v4.03)
Electrolytes (continued)			
Bicarbonate*	mmol/L	Decrease	Grade 0: \geq LLN Grade 1: < LLN – 16.0 mmol/L Grade 2: < 16.0 – 11.0 mmol/L Grade 3: < 11.0 – 8.0 mmol/L Grade 4: < 8.0 mmol/L
Phosphorus	mmol/L	Decrease	Grade 0: \geq LLN Grade 1: < LLN – 0.8 mmol/L Grade 2: < 0.8 – 0.6 mmol/L Grade 3: < 0.6 – 0.3 mmol/L Grade 4: < 0.3 mmol/L
Metabolic			
Glucose	mmol/L	Increase	Grade 0: \leq ULN Grade 1: > ULN – 8.9 mmol/L Grade 2: > 8.9 – 13.9 mmol/L Grade 3: > 13.9 – 27.8 mmol/L Grade 4: > 27.8 mmol/L
		Decrease	Grade 0: \geq LLN Grade 1: < LLN – 3.0 mmol/L Grade 2: < 3.0 – 2.2 mmol/L Grade 3: < 2.2 – 1.7 mmol/L Grade 4: < 1.7 mmol/L

LLN=lower limit of normal. ULN=upper limit of normal. The LLN and ULN for each analyte will be determined from the normal range of each local laboratory.

*Bicarbonate toxicity grade are taken from CTCAE v3.0.

6 Tables, Listings, and Figures

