3.10.1 Adverse Events

An AE is defined as any untoward medical occurrence in a patient or clinical investigation patient administered a pharmaceutical product, and that does not necessarily have a causal relationship with this treatment. An AE can therefore be any unfavorable and unintended sign (including an abnormal laboratory finding), symptom, or disease, temporally associated with the use of a medicinal (investigational) product, whether or not the AE is related to the medicinal (investigational) product. The term also covers laboratory findings or results of other diagnostic procedures that are considered to be clinically relevant as determined by the Investigator.

Analyses of AEs will be based on the principle of treatment emergence. Treatment-emergent AEs are defined as having onset after study drug dosing or a sign, symptom, or diagnosis that worsens after study drug dosing. Henceforth, whenever an analysis or summary of AEs is mentioned, it is intended that this is in reference to TEAEs, unless it is stated otherwise.

If AE start dates are completely missing or partially missing, the date imputation rules described previously in [Section 3.1.4](#) will be applied for the determination of treatment-emergence. This algorithm will be used only if the end date of the AE (if reported) indicates the event was not resolved before the first administration of study drug. Imputed AE dates will not be used to calculate the duration of AE episodes.

All AEs will be coded according to System Organ Class (SOC) and Preferred Term

(PT) using the Medical Dictionary for Regulatory Activities (MedDRA) dictionary (Version 19.0 or later).

For the escalation phase, the observed DLT rate in each dose cohort will be calculated by the crude proportion of patients who experienced DLT with a 2-sided, 95% exact binomial CI.

A summary of AEs, including incidences of:

- AEs
- SAEs
- AEs related to entinostat (“possibly related” or “related”)
- AEs related to avelumab (“possibly related” or “related”)
- AEs related to any study drug
- SAEs related to entinostat, avelumab, or both
- AEs leading to dose modification of entinostat, avelumab, or both
- AEs leading to discontinuation of entinostat, avelumab, or both
- AEs with a fatal outcome
- AEs with a CTCAE severity grade of Grade 3 or greater
- AEs with CTCAE severity of Grade 3 or greater related to entinostat, avelumab, or both

will be presented by dose cohort in Phase 1 and by treatment arm in Phase 2.

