6.3 List of Listings

Number	Title
Listing 16.2.1.1	Study Enrollment and Analysis Populations
Listing 16.2.1.2	Patients Not Evaluable for Efficacy or Safety Analysis
Listing 16.2.2.2	Study Disposition
Listing 16.2.2.3	Post-Treatment Follow-up
Listing 16.2.2.4	Post-Treatment Anti-Cancer Therapy
Listing 16.2.3.1	Exceptions to Protocol Eligibility Criteria
Listing 16.2.4.1	Demographic Characteristics
Listing 16.2.1.6	Ovarian Cancer History
Listing 16.2.1.7	Prior Systemic Anti-Cancer Therapy
Listing 16.2.1.8	Prior Surgery
Listing 16.2.1.9	Prior Radiation Therapy
Listing 16.2.1.10	Medical History
Listing 16.2.1.11	Entinostat Administration
Listing 16.2.1.12	Avelumab Administration
Listing 16.2.1.13	Concomitant Medications
Listing 16.2.1.14	Concomitant Procedures
Listing 16.2.1.15	Protocol Deviations

Listing 16.2.2.1	PK Plasma Concentrations for Entinostat
Listing 16.2.2.2	PK Plasma Concentrations for Avelumab
Listing 16.2.2.3	PK Parameters for Entinostat
Listing 16.2.2.4	PK Parameters for Avelumab
Listing 16.2.3.1	Adverse Events
Listing 16.2.3.2	Serious Adverse Events
Listing 16.2.3.3	Adverse Events with Action Taken of Dose of Either Drug Reduced, Held, or Discontinued Permanently
Listing 16.2.3.4	Deaths and Overall Survival
Listing 16.2.3.5	Clinical Laboratory Values – Hematology, WBC Count and Differential
Listing 16.2.3.6	Clinical Laboratory Values – Hematology, Erythrocytes and Platelets
Listing 16.2.3.7	Clinical Laboratory Values – Chemistry, Renal
Listing 16.2.3.8	Clinical Laboratory Values – Chemistry, Hepatic
Listing 16.2.3.9	Clinical Laboratory Values – Chemistry, Electrolytes
Listing 16.2.3.10	Clinical Laboratory Values – Metabolic
Listing 16.2.3.11	Patients with Laboratory Values Out of Normal Range with CTCAE Toxicity Grade
Listing 16.2.3.12	Vital Signs

Listing 16.2.3.13	12-Lead Electrocardiograms
Listing 16.2.3.14	ECOG Performance Status
Listing 16.2.3.15	Clinical Disease Assessments
Listing 16.2.4.1	Imaging
Listing 16.2.4.2	Target Lesions
Listing 16.2.4.3	Non-Target Lesions
Listing 16.2.4.4	New Lesions
Listing 16.2.4.5	RECIST 1.1 Response
Listing 16.2.4.6	irRECIST Response

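### Creatinine is graded only against the local upper limit of normal, so the tables that count patients miss or under-grade rises relative to the patient's own baseline

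*SAP*

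**What the plan says.** Section 3.10.2 of the SAP states that, where available, "laboratory values will be assigned toxicity grades using the NCI-CTCAE, version 4.03". Appendix 5.3 gives the cut-points. For creatinine, Grade 0 is at or below the ULN, Grade 1 is above it up to 1.5 times, Grade 2 is above 1.5 up to 3.0 times, and the top of the scale reads "Grade 3: $> 3.0 - 6.0 \times$ ULN Grade 4: $> 6.0 \times$ ULN". A footnote sets the reference limit: "The LLN and ULN for each analyte will be determined from the normal range of each local laboratory". Appendix 5.1 gives a standard creatinine range of 50 to 110 micromol/L, used only when the laboratory's own range is missing.

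Section 3.10.2 plans shifts relative to the local normal range and adds "Similar analyses will be performed for shifts in NCI CTCAE toxicity grades relative to the baseline toxicity grade". For chemistry these become Tables 14.4.11.2 and 14.4.12.2. The same section summarises baseline and the minimum, maximum, average and last post-baseline values, and says "Change from baseline for each of these post-baseline values will also be summarized". The listings in Section 6.3 include "Clinical Laboratory Values – Chemistry, Renal". Section 3.10.1 lets clinically relevant laboratory results be reported as adverse events.

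**The concern.** The shift tables are the planned laboratory displays that count patients with a worsening. Both use fixed limits: one asks whether the value left the normal range, the other whether it moved to a higher multiple of the ULN. Comparing with the baseline grade does not make the scale relative to baseline, because the baseline grade is itself set by the ULN. Two patients with the same relative rise can therefore get different grades, and a patient starting low in the range can have a large relative rise without appearing in either table. Safety measured partly by laboratory parameters is a stated secondary objective (Section 2.1.2), so a reader of the report may take these tables as a full count of creatinine worsening.

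**Working it through.** The plan states no figure to reproduce. The check applies the Appendix 5.3 cut-points to relative rises.

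**Inputs**
- Cut-points at 1.0, 1.5, 3.0 and 6.0 times the ULN (Appendix 5.3).
- A ULN of 110 and a lower limit of 50 micromol/L (Appendix 5.1), used as an illustration because local limits govern and are not given.
- Assumed local ULNs of 80 to 120 micromol/L, to show the range.
- Assumption: creatinine is among the tests selected for the shift tables.

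**Step 1: when does a doubling stay Grade 0?** Grade 0 requires 2 × baseline ≤ ULN, that is, baseline ≤ ULN/2. The value is then also at or below the upper limit, so the normal-range table shows no upward shift.

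| Assumed ULN | Doubling is Grade 0 for baselines up to |
|---|---|
| 80 | 40 |
| 90 | 45 |
| 100 | 50 |
| 110 | 55 |
| 120 | 60 |

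**Step 2: grade after a doubling, ULN 110**

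| Baseline | Doubled | Multiple of ULN | Grade |
|---|---|---|---|
| 50 | 100 | 0.91 | 0 |
| 55 | 110 | 1.00 | 0 |
| 56 | 112 | 1.02 | 1 |
| 60 | 120 | 1.09 | 1 |
| 80 | 160 | 1.45 | 1 |
| 82.5 | 165 | 1.50 | 1 |
| 83 | 166 | 1.51 | 2 |
| 110 | 220 | 2.00 | 2 |

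Within the range, a Grade 0 doubling covers baselines of 50 to 55: (55 − 50)/(110 − 50) = 8% of the range width. A doubling is at most Grade 1 for baselines up to 0.75 × 110 = 82.5: (82.5 − 50)/60 = 54% of the width. These are shares of the range, not of patients, because the SAP gives no baseline distribution.

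**Step 3: results that hold for any ULN.** If baseline ≤ ULN, then 3 × baseline ≤ 3.0 × ULN. Grade 3 needs more than 3.0 × ULN, so a tripling from any in-range baseline never reaches Grade 3. Likewise 1.5 × baseline ≤ 1.5 × ULN, so a 1.5-fold rise from an in-range baseline never reaches Grade 2. With a ULN of 110, that 1.5-fold rise is Grade 0 for baselines up to 110/1.5 = 73.3, and a tripling from 50 to 150 (150/110 = 1.36 × ULN) is Grade 1.

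**Step 4: effect on the two tables.** A rise from 50 to 100 is Grade 0 to Grade 0 and normal to normal, so neither table counts it. A rise from 50 to 150 is counted in both, but as Grade 1 in the grade-shift table.

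**The case against.** ULN-only grading is how Appendix 5.3 treats ALT, AST, alkaline phosphatase and bilirubin too, and any scale built on a limit gives different grades to equal relative rises. The rule is the same in both arms. The Grade 0 doubling is a corner of the range, and the 50 to 110 range is only a fallback. All of this stands, and it limits the size of the point.

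A reader might infer that renal toxicity goes under-reported in this trial, or that only a mean change would reveal such rises. The document does not support either. Change to the maximum post-baseline value is summarised, and Section 3.1.2 requires its median, minimum and maximum as well as its mean. Renal values are listed per patient. On adverse events, Section 3.10.1 says "The term also covers laboratory findings or results of other diagnostic procedures that are considered to be clinically relevant as determined by the Investigator", and those events are counted by preferred term and severity. BUN is also listed as a renal analyte with a normal range. What remains is that none of these systematically counts patients by relative creatinine rise: adverse events depend on investigator judgement, and the summaries and listings do not give a count.

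A reader might also infer that patients in this trial tend to start low in the range, or that the row departs from CTCAE v4.03. The SAP gives no baseline creatinine data and does not reproduce the v4.03 text, so neither can be claimed here.

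Replacing the grade with a home-made hybrid would create its own problem: 50 rising to 76 (76/50 = 1.52 times baseline) would become Grade 2 while mid-normal, under a column headed CTCAE v4.03. That is a sound reason to show relative rises beside the ULN grade unless the named version itself calls for more.

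**Conclusion.** The point holds in a limited form. The creatinine grade-shift table misses or under-grades rises relative to the patient's own baseline, and the normal-range table misses those that stay in range. The tripling result follows from the cut-points for any ULN, given an in-range baseline. The Grade 0 doubling depends on the local ULN and reaches baselines of 40 to 60 micromol/L over the assumed ULNs of 80 to 120. How many patients this would touch cannot be estimated from the SAP. The issue is confined to descriptive safety tables; PFS, its alpha and its power are unaffected. It is a cheap improvement to patient-level safety counts and does not show that the plan hides renal toxicity.

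**What to change.** Keep the ULN grades. Add to the creatinine part of Table 14.4.12.2, per arm, the number and percentage of patients whose worst post-baseline value is above 1.5 and up to 3.0 times baseline, and above 3.0 times baseline. These are the row's own multiples applied to baseline as defined in Section 3.1.3, with the denominator already set in Section 3.10.2.

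Before programming, verify the creatinine row against the CTCAE version named in the column header. If that version includes a baseline criterion, grade by the worse of the two. The check is reasonable in any case, since the footnote to Appendix 5.3 takes the bicarbonate grades from v3.0 under the same v4.03 header.

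The cost is one extra programming condition on data already collected. The downside is somewhat more creatinine findings on display, some of them within the normal range, so the added lines should be labelled as relative to baseline.
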